### 5.3 Planned analysis

- **Part 1:**

- PK analysis will be described in the separate PK analysis plan
- Safety data will be reviewed during a Safety Data Review Meeting between the Sponsor and the investigator. The following safety data will be reviewed: Vital Signs (heart rate, blood pressure, respiratory rate, and pulse oximetry), Tympanic temperature, Physical examination, Safety laboratory values, Urinalysis, Adverse events, Serious Adverse events and Concomitant medication use.

- **Part 2:**

- All statistical analysis are described below.
- The list of statistical Tables, Figures and Listings are provided in Section 11.
- Efficacy analysis will be on the evaluable population. The safety evaluation will be performed on the SAF population.

#### 5.3.1 Subject disposition and study discontinuations

Subject disposition will be described using a table (Statistical table 14.1.1). The following variables will be tabulated:

- Number of enrolled patients
- Number of randomized subjects
- Number of randomized subjects per treatment group

Study populations will be tabulated, total and per treatment group (Statistical table 14.1.2.1) along with reasons for exclusion from the Evaluable, SAF and PK analysis populations (Statistical tables 14.1.2.2, 14.1.2.3 and 14.1.2.4 respectively).

Study duration and premature study discontinuation will be summarized using the following variables (Statistical table 14.1.3) on SAF population:

- Number of subjects who completed/discontinued the study, total and per treatment group
- Reason of study discontinuation, total and per treatment group
- Study duration, total and per treatment group

 Venn Life Sciences <small>Think Research</small>	Document Number or Project Identification: VH0001 / MB05-P-01-20
	Document Version: v3
Statistical Analysis Plan	

All reason for study discontinuation will also be presented in the Listing 16.2.1 along with end of study information.

Visit dates (including date of consent) will be presented in Listing 16.2.4.13.

Population membership and reason for exclusion will be also provided in Listing 16.2.3.

### 5.3.2 Protocol deviations

All major and minor protocol deviations classified during the data-review meeting will be described in Statistical table 14.1.4 on SAF population and also be provided in Listing 16.2.2.

### 5.3.3 Demographics and baseline characteristics

The following demographics variables will be summarized by treatment group on the Evaluable and SAF populations (Statistical table 14.1.5 and Listing 16.2.4.1):

- Gender
- Age
- Ethnicity

The following baseline characteristics will be summarized by treatment group on SAF population:

- Weight, Height and BMI (Statistical table 14.1.6 and Listing 16.2.4.2)
- Alcohol breath test (Statistical table 14.1.7 and Listing 16.2.4.3)
- Urine drugs of abuse (Statistical table 14.1.8 and Listing 16.2.4.4)
- Urine pregnancy test (Statistical table 14.1.9 and Listing 16.2.4.5)
- Patient Health Questionnaire (PHQ-9) (Statistical table 14.1.10 and Listing 16.2.4.6)
- Generalised Anxiety Disorder Questionnaire (GAD-7) (Statistical table 14.1.11 and Listing 16.2.4.7)
- HIV, Hepatitis A, B & C (Statistical table 14.1.12 and Listing 16.2.4.8)
- Thyroid function test (Statistical table 14.1.13 and Listing 16.2.4.9)

Eligibility criteria, randomisation information will be presented respectively in Listings 16.2.4.10 and 16.2.4.11)

Nasopharyngeal swab / nasal swab respiratory Pathogen Screen data (including COVID-19 test) will be presented in listing 16.2.4.14.

### 5.3.4 Medical history – Previous medications

Medical history will be presented by SOC & PT by treatment group (Statistical table 14.1.14).

Previous medications will be presented by ATC code and Preferred Name by treatment group (Statistical table 14.1.15)

Medical history for each subject will be reported in Listings 16.2.4.12.

## 5.4 Efficacy analyses

### 5.4.1 Primary efficacy analysis

#### **Objective 1:**

To estimate the margin and variance of prophylactic effect of Intravenous (IV) treatment with Palivizumab administered 1 day prior to inoculation in the RSV human challenge model in healthy

 Venn Life Sciences Think Research	Document Number or Project Identification: VH0001 / MB05-P-01-20
	Document Version: v3
Statistical Analysis Plan	

adults compared to Placebo [assessed by quantitative reverse transcriptase-polymerase chain reaction (qRT-PCR)].

Area under the viral load-time curve (VL-AUC) of RSV-A Memphis 37b as determined by **qRT-PCR** on nasal samples collected twice daily starting two days post-viral challenge (Day +2) up to the end of quarantine will be calculated (using the trapezium rule) and tabulated per treatment group. Treatment groups will be compared using t-test if assumptions are valid (Statistical Table 14.2.1.1). In case of distribution not normal, a data transformation could be used.

qRT-PCR will be also tabulated per visit/timepoint for each treatment group (Statistical Table 14.2.1.2).

Spaghetti plots and mean value over time will be used for graphical presentation of qRT-PCR, boxplot will be used for AUC presentation (Statistical Figures 14.2.1.1 to 14.2.1.3).

Individual data for qRT-PCR (included derived data) will be presented on Listing 16.2.6.1.

## 5.4.2 Secondary efficacy analyses

### 5.4.2.1 Viral loads/shedding evaluations

#### a) **Objective 2:**

To estimate the margin and variance of prophylactic effect of IV treatment with Palivizumab administered 1 day prior to inoculation in the RSV human challenge model in healthy adults compared to Placebo [assessed by cell culture (pfu/mL)].

Area under the viral load-time curve (VL-AUC) of RSV-A Memphis 37b as determined by **cell culture** on nasal samples collected twice daily starting two days post-viral challenge (Day +2) up to the end of quarantine will be calculated (using the trapezium rule) and tabulated per treatment group. Treatment groups will be compared using t-test if assumptions are valid (Statistical Table 14.2.2.1). In case of distribution not normal, a data transformation could be used.

Cell culture will be also tabulated per visit/timepoint for each treatment group (Statistical Table 14.2.2.2).

Spaghetti plots and mean value over time will be used for graphical presentation of cell culture, boxplot will be used for AUC presentation (Statistical Figures 14.2.2.1 to 14.2.2.3).

Individual data for cell culture (included derived data) will be presented on Listing 16.2.6.2.

#### b) **Objective 6**

Peak viral load of RSV-A Memphis 37b as defined by the maximum viral load determined by quantifiable qRT PCR measurements in nasal samples starting two days post viral challenge (Day +2) up to the end of quarantine will be calculated and presented by treatment group and compared using t-test if assumptions are valid (Statistical Table 14.2.3.1). In case of distribution not normal, a data transformation could be used.

Peak viral load of RSV-A Memphis 37b will be also described graphically using boxplot (Statistical Figure 14.2.1.4).

 Venn Life Sciences <small>Think Research</small>	Document Number or Project Identification: VH0001 / MB05-P-01-20
	Document Version: v3
Statistical Analysis Plan	

Peak viral load of RSV-A Memphis 37b as defined by the maximum viral load determined by quantifiable cell culture measurements in nasal samples starting two days post viral challenge (Day +2) up to the end of quarantine will be calculated and presented by treatment group and compared using test test if assumptions are valid (Statistical Table 14.2.3.2).

Peak viral load of RSV-A Memphis 37b will be also described graphically using boxplot (Statistical Figure 14.2.2.4).

Number of days with quantifiable qRT PCR measurements in nasal samples starting two days post viral challenge (Day +2) up to the end of quarantine will be calculated and presented by treatment group and compared using t-test if assumptions are valid (Statistical Table 14.2.4.1). In case of distribution not normal, a data transformation could be used. In case of missing data on at least one visit, the number of days will be considered as missing for the subject, except if quantifiable measurement is already recorded on other timepoint for this visit..

Number of days with quantifiable cell culture measurements in nasal samples starting two days post viral challenge (Day +2) up to the end of quarantine will be calculated and presented by treatment group and compared using t-test if assumptions are valid (Statistical Table 14.2.4.2). In case of distribution not normal, a data transformation could be used. In case of missing data on at least one visit, the number of days will be considered as missing for the subject, except if quantifiable measurement is already recorded on other timepoint for this visit..

Duration of virus shedding will be analysed using Kaplan-Meier method. A Kaplan-Meier plot by treatment group will be displayed showing the duration of virus shedding (with the time axis as days since first virus shedding). A table will accompany the plot and will display the Kaplan-Meier estimates of the cumulative proportion of subjects' event free at specific time points by treatment group. Subjects who did not have a confirmed undetectable measure after their peak, will be censored at their last detectable assessment. Subjects who do not have a detectable value during quarantine (including any extended quarantine period) will be excluded from the analysis (Statistical Table 14.2.4.3 & Statistical Figure 14.2.3).

Time to Peak Virus Shedding will be described by treatment group. If the peak value is seen on more than one day, the first occurrence is used. Subjects who do not have a detectable value during quarantine (including any extended quarantine period) will be excluded from the analysis. (Statistical Table 14.2.4.4).

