### 4.2.1.4 Incidence of infection & illness

- Objective 6:
  - Incidence of laboratory-confirmed infection (variant 1 as below)
  - Incidence of laboratory-confirmed infection (variant 2 as below)
- Objective 7:
  - “Laboratory-confirmed virus-like-illness” (variant 3, as below), as defined by:
    - Incidence of “laboratory-confirmed infection”, and
    - At least one grade 2 symptom from one or more respiratory categories from the participant symptom diary card
  - “Laboratory-confirmed virus-like-illness” (variant 1, as below)
  - “Laboratory-confirmed virus-like-illness” (variant 2, as below)
  - Upper respiratory tract illness (URTI)
  - Lower respiratory tract illness (LRTI)
  - Systemic illness (SI)
  - Febrile Illness (FI)
  - Fold seroconversion

Laboratory-confirmed infection

“Laboratory-confirmed infection” is defined as the presence of “viral shedding”, measured in nasal samples. Subjects with incomplete qPCR data and no recorded data meeting the definition will be treated as not having met the criteria for Laboratory-confirmed RSV infection.

Viral shedding (variant 1)

One or both of the following definitions must be met:

- At least 2 positive quantifiable detections by viral load qPCR assay specific for the challenge virus, reported within 4 consecutive scheduled assessments and from 2 independent samples from Day +2 until discharge (For clarification, see some examples in table below)

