**Examples of Viral Load qPCR Assay Values (only) and Evidence of Viral Shedding.**

Assessment n#	Assessment n+1*	Assessment n+2*	Assessment n+3*	Viral shedding?
Detected	Detected	Detected	Detected	No
1.456	2.359	Any value	Any value	Yes
0.956	Detected	3.647	Any value	Yes
3.452	Not detected	Detected	0.956	Yes
Not Detected	2.359	Not detected	4.852	Yes
Not Detected	1.128	3.647	Not detected	Yes
1.567	Not detected	Not detected	Detected	No
1.5567	Not detected	Not detected	2.434	Yes

qPCR data are scheduled to be collected twice daily (morning and evening).

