# Assessment n may be on the morning or evening of any given day.

\* n+1, n+2 and n+3 are the scheduled assessments following assessment n and independent of study day. For example, Assessment n could be Day 2 evening and Assessment n+3 could be Day 4 morning.

- One positive detection by viral load qPCR assay, specific for the challenge virus, in which an aliquot of the same sample has also tested positive in a viral culture assay appropriate for detecting the challenge virus (i.e. cell-based infectivity assay) from Day +2 until discharge.

For qPCR and the cell-based infectivity assay, a positive detection is any positive numeric or ‘Detected’ value. A quantifiable detection value is any numeric value and will exclude ‘Detected’ and ‘Not detected’ values.

Viral shedding (variant 2)

One or both of the following definitions must be met:

- At least 2 positive detectable assessments by viral load qPCR assay specific for the challenge virus, reported within 4 consecutive scheduled assessments and from 2 independent samples from Day +2 until discharge
- One positive detection by viral load qPCR assay, specific for the challenge virus, in which an aliquot of the same sample has also tested positive in a viral culture assay appropriate for detecting the challenge virus (i.e. cell-based infectivity assay) from Day +2 until discharge.

Laboratory-confirmed virus-like-illness (variant 1)

Virus-like-illness (variant 1) is defined as the occurrence of laboratory-confirmed infection AND any of the following:

- Upper respiratory tract illness (defined below)

 Venn Life Sciences <small>Think Research</small>	Document Number or Project Identification: VH0001 / MB05-P-01-20
	Document Version: v3
Statistical Analysis Plan	

- Lower respiratory tract illness (defined below)
- Systemic illness (defined below)
- Febrile illness (defined below).

Laboratory-confirmed virus-like-illness (variant 2)

Virus-like-illness (variant 2) is defined as the occurrence of laboratory-confirmed infection AND symptoms of either of the following:

- any two different self-reported diary card symptoms ( $\geq$  Grade 1), or
- at least one Grade 2 self-reported symptom from one or more respiratory categories (URTI and LRTI symptoms defined below).

Laboratory-confirmed virus-like-illness (variant 3)

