## Statistical Analysis Plan

- Assignations based on dates will be reviewed and confirmed or infirmed during the data review meeting
- Missing or partial start or end dates of IMP administration, if any, will be reviewed during the data review meeting.
- No other missing data will be imputed except if otherwise specified in Section 4, Section 5.3to 5.6.

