### 5.2.3.2 Analysis rules

Analysis	Associated Units	Assay LLOD	Assay LLOQ	Result	Reported results	Analysis value
RSV titre (qRT-PCR)	Log10 Copies/mL	NA	2.8*	Quantifiable Titre	Value	Reported value
				DETECTED	DETECTED	LLOQ/2
				NOT DETECTED	NOT DETECTED	0
				INVALID	INVALID	Missing data point
				NOT TESTED	NOT TESTED	Missing data point
RSV titre (Plaque assay)	Log10 PFU/mL		1.7	Quantifiable Titre	Value	Reported value
				>6.04	>6.04	6.04 (ULOQ)
				DETECTED	DETECTED	LLOQ/2
				NOT DETECTED	NOT DETECTED	0
				INVALID	INVALID	Missing data point
RSV antibody titre	NAb	10	156	NDA	NDA	LLOD
				>=10 and <156	<156	LLOQ/2
				Quantifiable Titre	Value	Reported value
				≥4209	≥4209	4209 (ULOQ)
				INVALID	INVALID	Missing data point
				NOT TESTED	NOT TESTED	Missing data point

\*The LLOQ is defined as a cycle threshold (Ct) value of 33.9. This equated to 2.8 Log10 copies/mL by utilisation of a target specific copy number standard curve included in each assay run of the assay validation.

NA: Not Applicable

NDA: No Detectable Antibody

PFU: Plaque Forming Units

 Venn Life Sciences <small>Think Research</small>	Document Number or Project Identification: VH0001 / MB05-P-01-20
	Document Version: v3
Statistical Analysis Plan	

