**c) Objective 7**

Peak symptom score defined by the maximum daily sum of Symptom score starting one day post viral challenge (Day +1) up to the end of quarantine will be determined and tabulated per treatment group. Treatment groups will be compared using t-test if assumptions are valid (Statistical Table 14.2.6.1). In case of distribution not normal, a data transformation could be used.

Peak symptom score will be also described graphically using boxplot (Statistical Figure 14.2.4.4).

Number of days with symptoms of grade 2 or more, starting one day post viral challenge (Day +1) up to the end of quarantine will be calculated and tabulated per treatment group. Treatment groups will be compared using t-test if assumptions are valid (Statistical Table 14.2.6.2). In case of distribution not normal, a data transformation could be used. In case of missing data on at least one visit, the number of days will be considered as missing for the subject, except if grade 2 or more is already recorded on other timepoint for this visit.

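### The missing-data rule for the number-of-days endpoints drops participants according to outcome: one missing sample or card removes the whole participant unless that day is already positive

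*SAP*

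**What the plan says.** SAP 5.4.2.1 b) defines the number of days with quantifiable qRT-PCR results, and separately with quantifiable culture results, from Day +2 to the end of quarantine. For both it says: "In case of missing data on at least one visit, the number of days will be considered as missing for the subject". A single escape clause is attached to that rule and is worded as follows: "except if quantifiable measurement is already recorded on other timepoint for this visit". The exception only makes sense if one missing timepoint is enough to trigger the rule. SAP 5.4.2.2 c) repeats the rule for days with grade 2 or worse symptoms, with its own escape clause: "except if grade 2 or more is already recorded on other timepoint for this visit".

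Three other provisions determine how often this applies:

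- SAP 4.2.1.4: "A quantifiable detection value is any numeric value". Results reported only as detected or not detected are excluded, so neither rescues a day.
- SAP 5.2.3.2: an INVALID result in either assay, or a NOT TESTED qRT-PCR result, is a "Missing data point". Laboratory failures therefore trigger the rule as well as missed swabs.
- SAP 5.2.3.1: "No other missing data will be imputed except if otherwise specified".

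The incidence endpoints follow a different convention. For laboratory-confirmed infection, SAP 4.2.1.4 says: "Subjects with incomplete qPCR data and no recorded data meeting the definition will be treated as not having met the criteria". The same section handles the proportions with grade 2 or worse symptoms in the same way: incomplete data with nothing recorded counts as not meeting the endpoint, and the participant is kept.

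**The concern.** A gap on a shedding day is forgiven if the other swab that day is quantifiable. The same gap on a day whose other swab is a valid negative removes the participant from the analysis, with every other valid sample. Participants with many negative days carry most of this risk, so the retained set is enriched for shedders in both arms. If palivizumab works as Protocol 9.1 hypothesises, its arm has more negative days and loses more participants.

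This matters because the Part 2 objectives are to estimate the margin and variance of the effect, for use in later biosimilar comparisons (Protocol 2.2). Arm means, SDs and the relative reduction are the quantities such planning would use. With 25 per arm, avoidable losses also cost precision.

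**Working it through.** **Plan figure.** The plan gives no expected value, power or missing-sample rate for these endpoints, so there is no figure of its own to reproduce. The 25 per arm in Protocol 9.2.2 is sized on VL-AUC and does reproduce from its stated inputs (mean 20.3, SD 17.8, 70% reduction, 80% power, two-sided 5%).

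**Inputs from the documents.** Swabs are taken twice daily on Days 2 to 11 and once on Day 12 (Protocol 1.3.2): 10 × 2 + 1 = 21, for discharge on Day 12. Diary cards are completed three times daily on Days 1 to 11 and once on Day 12: 11 × 3 + 1 = 34. The placebo infection rate is 73.7% (Protocol 9.2.2).

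**Assumptions.** Each sample is missing independently with probability q. A shedder has D = 6 days with both swabs quantifiable and no other quantifiable swab. All 73.7% of placebo participants are shedders in this sense. The palivizumab shedding rate is 22.1% (0.3 × 73.7%).

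**Step 1: probability of being kept.**
- Non-shedder: (1−q)^21.
- Shedder with D days: (1−q²)^D × (1−q)^(2(10−D)+1). For D = 6 this is (1−q²)^6 × (1−q)^9.
- At q = 2%: non-shedder 0.98^21 = 0.654; shedder 0.9976 × 0.8337 = 0.832.

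| q | Non-shedders dropped | Six-day shedders dropped |
|---|---|---|
| 0.5% | 10.0% | 4.4% |
| 1% | 19.0% | 8.7% |
| 2% | 34.6% | 16.8% |

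For diary cards, 1 − 0.99^34 = 28.9% of participants with no grade 2 symptom would be dropped at 1% missing.

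**Step 2: arm level at q = 2%.**
- Placebo kept: 0.737 × 0.832 + 0.263 × 0.654 = 0.785, so 21.5% are lost (5.4 of 25). The mean moves from 6 × 0.737 = 4.42 to 6 × 0.613/0.785 = 4.68 days.
- Palivizumab kept: 0.221 × 0.832 + 0.779 × 0.654 = 0.693, so 30.7% are lost (7.7 of 25). The mean moves from 1.33 to 6 × 0.184/0.693 = 1.59 days.
- SD, as 6 × √(π(1−π)) with π the proportion of shedders among those kept: placebo 2.64 to 2.48; palivizumab 2.49 to 2.65.
- Relative reduction: 70.0% to 1 − 1.59/4.68 = 66%.
- Difference in means: 3.10 before and 3.10 after.
- Standard error of the difference: √((2.64² + 2.49²)/25) = 0.726 with nobody dropped; √(2.48²/19.6 + 2.65²/17.3) = 0.848 under the rule, about 17% larger.

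At q = 0.5% the losses are 5.9% and 8.8% (1.5 and 2.2 of 25), and the standard error grows by about 4%.

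**Step 3: sensitivity to the assumptions.** With five shedding days in both arms and q = 2%, the difference moves from 2.19 to 2.15 days if 30% shed on palivizumab, and from 3.19 to 3.27 if 10% do. If treated shedders also shed for a shorter time (2 days against 5, with 40% shedding), it moves from 2.88 to 3.03 and the relative reduction stays at 78.3%. With equal shedding in both arms, losses are equal. In a simulation of 4,000 trials per setting (40% shedding on palivizumab; shedder days Poisson with mean 5, limited to 1–10), t-test power falls from 0.52 with no deletion to 0.45 at q = 1% and 0.40 at q = 2%.

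**The case against.** The strongest reply is that the planned comparison is hardly biased. SAP 5.1.2 and 5.4.2.1 compare the groups by t-test on the difference in means, and in the main calculation that difference does not move. A reader might infer that the rule biases the treatment comparison against palivizumab. The numbers do not support that: both means rise by about the same number of days, and under other assumptions the difference can move slightly either way. This part of the reply stands.

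The size is also uncertain. Participants are resident and sampled on a schedule, the Evaluable set requires completing quarantine, and SAP 5.4.2.2 a) expects no missing diary data. At 0.25% missing, about 5% of non-shedders and 2% of six-day shedders would be lost, roughly one participant per arm. Clustered gaps would delete fewer participants than independent ones. The 22.1% carries a VL-AUC reduction over to infection, which the plan does not assume. The 73.7% corresponds to detectable infection (SAP version history, V2), which is looser than six fully quantifiable days. All of this stands, and a loss near a third of an arm should not be read as expected.

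These are secondary endpoints in an exploratory study. VL-AUC and the Kaplan-Meier duration of shedding do not use this rule, and the infected-subgroup tables leave out participants in whom virus was never detected. That also stands.

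One might call the two missing-data conventions a contradiction. They are not strictly one: SAP 5.2.3.1 allows endpoint-specific rules, and a yes/no endpoint differs from a count. They are inconsistent in effect, since the same incomplete record can count as uninfected in one table and be absent from the next.

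Declining to assign a count that was not fully observed is defensible in principle. What does not survive is the asymmetry: the rule accepts a partly observed day when it is positive and rejects it when it is negative.

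**Conclusion.** The point holds as a defect in a secondary-endpoint rule, of minor to moderate weight. Outcome-dependent deletion follows from the wording for any missing rate above zero. It discards valid data, pushes both arm means upward, shifts the SDs, can attenuate the relative reduction, and costs precision at 25 per arm. Under the stated assumptions the cost runs from about 6% and 9% of the arms lost at 0.5% missing to 21.5% and 30.7% at 2%. The excess loss on palivizumab depends on palivizumab reducing shedding; with no effect there is none. A material bias in the difference in means is not shown. No sensitivity analysis for this rule is planned, so the reported tables would not reveal its influence.

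**What to change.** Replace the rule in SAP 5.4.2.1 b) (qRT-PCR and culture) and 5.4.2.2 c) before unblinding:

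- A day with at least one valid sample or card is positive if any valid one is quantifiable (or grade 2 or worse), and negative otherwise.
- No participant is set to missing for isolated gaps.
- State a rule for wholly missing days. One option is to count such a day as positive only if both adjacent days are positive. Day 12 has one scheduled swab and no later scheduled neighbour, so it needs its own line.
- Report bounds that count all unobserved samples or cards first as negative and then as positive, and give the number of missing samples by arm.

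The cost is a short SAP amendment and minor programming. The day count will be slightly low when the missing sample was the only positive one that day; the bounds cover this. If missingness proves negligible, the results hardly change.
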